8.4 Procedure at disease progression

Progression events should be imaging defined in all tumour types according to RECIST criteria. In addition, for prostate cancer patients progression by bone scan and PSA progression will be considered. On the rare occasions that progression cannot be measured by scan or biochemical failure (prostate only), clinical evidence of widespread progression will count as a PFS event.

Participants should be treated according to local clinical judgement at disease progression. Following progression, participants will continue to be followed-up for FFWM and overall survival. Imaging and visits following progression can be according to local practice and do not need to follow the protocol specified visit time points, however information regarding FFWM and survival status should be entered onto the eCRFs.

The FFWM endpoint is defined as radiological evidence that the patient has 4 or more metastatic sites and/or the site(s) of disease progression are not suitable for radical salvage therapy (e.g. surgery, RFA or SBRT).

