3 TRIAL DESIGN

CORE is a phase II/III, multi-centre, non-blinded, parallel group randomised controlled trial in patients with breast, prostate or NSCLC primary cancer comparing standard of care (SOC) with or without SBRT for extra-cranial metastases. The aim of the phase II study is to demonstrate 1) feasibility of recruitment, 2) deliverability of the study in a multi-centre setting and 3) activity of SBRT, based on progression free survival, across the three tumour types. If all three aims are achieved the trial will be amended to roll into parallel tumour-site specific phase III trials.

Eligible patients are those with either primary breast, prostate or NSCLC who have presented with ≤ 3 extra-cranial, metachronous, oligometastases, all suitable for SBRT. Patients will be randomised in a 1:1 ratio to either SOC or SOC with the addition of SBRT. Choice of SOC treatment is at the discretion of the local oncologist and defined per patient prior to randomisation (see Section 9 Trial Treatment). Patients randomised to SBRT+SOC will receive a dose and fractionation regimen dependent on the metastatic site and proximity to dose limiting organs and normal tissues. Treatment will take place within 6 weeks of randomisation. The average scheme would be 3 treatments over 5 days but the maximum period of SBRT duration could be 8 treatments over 19 days.

All patients will be reviewed every 3 months with a clinical examination and tumour markers (where applicable) during years 1 and 2, and 6 monthly thereafter to 5 years. Staging and follow up imaging protocols will be tumour type dependent:

- **Breast:** 3 monthly CT scans for years 1 and 2, and 6 monthly thereafter to 5 years.
- **NSCLC:** 3 monthly CT scans for years 1 and 2, 6 monthly to year 3, then annually to 5 years.
- **Prostate:** CT scans will be performed at 6, 12 and 24 months with imaging triggered by appropriate PSA rises. A rising PSA defined as 2 successive PSA rises from nadir, measured a minimum of 4 weeks apart, will be used to trigger additional imaging (CT) between these time points.

All patients will have a toxicity assessment at each clinic visit and patient reported quality of life (QOL) assessment at 3, 6, 12, 18 and 24 months.

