9.1.6 Repeat SBRT

Only those patients allocated SBRT treatment at randomisation should be offered repeat SBRT treatment upon development of new extra-cranial lesions, where the total number of metastatic lesions over time since diagnosis of metastatic disease remains ≤ 3 , and the primary site and other sites previously treated with SBRT are under control. Suitability of new lesions for further SBRT will be based on the same criteria as at trial entry (visible, imaging defined targets suitable for SBRT, $\leq 6\text{cm}$ ($\leq 5\text{cm}$ for lung metastases)). Where multiple lesions are treated over the course of the trial, composite dose volume data must be assessed and all normal tissue dose constraints need to be met by the composite plan. Particular caution is required where isodose lines overlap serial organs. Any previous radiotherapy before trial entry should also be taken into account. 50% isodose lines for plans to individual lesions should not overlap. A period >3 months since the last SBRT treatment is required before commencing repeat SBRT.

Re-irradiation

Further SBRT treatment of lesions previously treated with SBRT either as part of the trial or prior to trial entry is not permitted in the CORE trial.

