10 SAFETY REPORTING

10.1 Definitions

Adverse Event (AE)

An AE is any untoward medical occurrence in a patient administered a study treatment; the event does not necessarily have a causal relationship with the treatment.

For the purpose of this trial, any detrimental change in the patient's condition subsequent to the start of the trial (i.e. randomisation) and during the follow-up period should be considered as an AE.

Serious Adverse Event (SAE)

An SAE is any untoward medical occurrence that occurs after randomisation and within the following 90 days and:

- results in death,
- is life-threatening
- requires hospitalisation or prolongation of existing inpatients' hospitalisation
- results in persistent or significant disability or incapacity
- is a congenital anomaly or birth defect

In addition, any radiotherapy related grade ≥ 4 events occurring between 90 days after randomisation and 5 years after randomisation should be reported according to serious adverse event reporting timelines.

Important adverse events that are not immediately life-threatening or do not result in death or hospitalisation but may jeopardise the subject or may require intervention to prevent one of the other outcomes listed in the definition above, may also be considered serious.

Progression of the indicated disease and death due to progression of the indicated disease are not considered SAEs.

Pregnancy or aid in the conception of a child whilst participating in a trial is not itself considered an SAE but should be followed up for congenital anomalies or birth defects.

Serious Adverse Reaction (SAR)

A serious adverse reaction is an SAE that is suspected as having a causal relationship to trial treatment, which for the purposes of this trial will be SBRT, as assessed by the investigator responsible for the care of the patient. A suspected causal relationship is defined as possibly, probably or definitely related (see definitions of causality table).

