11.2.2 Secondary endpoints

Recruitment rate is defined as the proportion of patients recruited to the trial. The denominator is the total number of patients required (i.e. 206 patients).

SBRT delivery is based on the proportion of patients allocated SBRT who received SBRT in the absence of new developing widespread disease and within the dosimetric constraints outlined in the SBRT protocol. The denominator is the number of patients allocated SBRT.

Overall survival is defined as time from randomisation until the time of death from any cause

Local lesion control is defined as time from randomisation until radiological evidence of progression at the treated site.

Clinician reported acute and late radiation related toxicity will be graded using NCI CTCAE v4.0/RTOG systems. Acute events are defined as those occurring up to 3 months follow up; late events are reported from 6 months post randomisation.

Patient reported quality of life will be measured using the EORTC QLQ C30 and EQ5D.

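### After progression, section 8.4 no longer secures scheduled grading of lower-grade toxicity, and acute reactions to repeat SBRT have no correct acute/late category

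*Protocol*

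**What the plan says.** **After progression (8.4).** The stated purpose of continued follow-up is limited: "Following progression, participants will continue to be followed-up for FFWM and overall survival". The visit timetable is released: "Imaging and visits following progression can be according to local practice and do not need to follow the protocol specified visit time points". The data still required are then named: "however information regarding FFWM and survival status should be entered onto the eCRFs". Toxicity does not appear. Section 8.5 sends patients who discontinue treatment to the same rule, and unacceptable toxicity is one of its listed reasons for discontinuation.

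**Toxicity elsewhere.** Section 3 states "All patients will have a toxicity assessment at each clinic visit". Sections 8.3.2 to 8.3.4 schedule CTCAE and RTOG assessment at follow-up visits to month 60. Section 10.1 counts AEs from randomisation through follow-up, and 10.3 requires every AE on a CRF. Section 11.2.4 gives SBRT-related, non-haematological grade 2 or higher toxicity as the main interest and compares arms by Fisher's exact test.

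**Serious events.** Section 10.1 sets the general window: "An SAE is any untoward medical occurrence that occurs after randomisation and within the following 90 days". Beyond day 90 and up to 5 years, 10.1 keeps radiotherapy-related grade 4 or higher events reportable. For the same period, 10.4 speaks of radiotherapy-related SAEs in patients receiving SBRT.

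**Repeat SBRT (9.1.6).** "Only those patients allocated SBRT treatment at randomisation should be offered repeat SBRT treatment upon development of new extra-cranial lesions", subject to a lifetime total of no more than 3 lesions. Timing: "A period >3 months since the last SBRT treatment is required before commencing repeat SBRT". Section 11.2.2 counts acute events up to 3 months of follow-up, and "late events are reported from 6 months post randomisation". Neither definition mentions a repeat course.

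**The concern.** A site that follows 8.4 to the letter can return no scheduled grade 2 or 3 toxicity for a patient who has progressed, while sections 3, 8.3, 10.1 and 10.3 imply that grading continues. Sites may resolve that conflict differently.

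Two things are at stake:

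- **The toxicity comparison.** Fisher's exact test on the proportion with a grade 2 or higher event makes no allowance for time under observation. If SBRT delays progression, its patients stay on scheduled grading longer, and the arms are compared over unequal observation.
- **Repeat courses.** An acute reaction to a second course cannot be recorded as acute. It either enters the late-toxicity count or falls between the two categories. A grade 4/5 reaction classed as late also counts toward the 5% criterion in 11.2.5.

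**Working it through.** **1. Planning inputs (11.1.2), checked first.** Control median 16 months, hazard ratio 0.75, one-sided alpha 0.20, power 80%, 138 events.

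- Weighted control median: 0.75×18 + 0.14×12 + 0.11×5 = 15.73, stated as 16.
- Events by Schoenfeld's formula: 4(0.8416 + 0.8416)² / (ln 0.75)² = 136.9, so 137. Freedman's formula gives 139. The stated 138 is reproduced.

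**2. Share still event-free, and so not released by 8.4 on progression.** Assume exponential PFS: S(t) = 0.5^(t/median), with medians 16 (SOC) and 16/0.75 = 21.33 months (SBRT).

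| Month | SBRT | SOC |
|---|---|---|
| 6 | 0.5^(6/21.33) = 82% | 0.5^(6/16) = 77% |
| 12 | 68% | 60% |
| 24 | 46% | 35% |
| 60 | 14% | 7% |

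Averaging 1 − S(t) over the 13 planned visits from month 6 to month 60, about 55% (SBRT) and 64% (SOC) fall after a PFS event. Over the 7 visits from month 6 to month 24, the shares are about 37% and 46%.

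Sensitivity at 6 and 24 months:

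- SBRT median of 20 months (the 4-month gain in 11.1.2): SBRT 81% and 44%.
- Mixture of the three tumour-site medians: SBRT 80% and 43%, SOC 74% and 34%.

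These are event-free shares, and PFS includes death. A patient who has died could not have been graded under any wording, and some sites will go on grading. The complements are therefore upper bounds on what 8.4 can lose. The difference between arms rests on the assumed hazard ratio; with no PFS effect it would vanish.

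**3. Repeat SBRT always follows progression and day 90.**

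- It is triggered by a new lesion. Appendix A1.4 counts a new lesion as progressive disease, and 11.2.1 counts progression at any site as a PFS event.
- The shortest schedule in 9.1.4 has 3 fractions, daily at the fastest, so the last fraction is at least 2 days after the first, which follows randomisation. Three calendar months are at least 89 days, and the gap must exceed that. The repeat course thus starts later than day 2 + 89 = 91, outside the 90-day window.

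**4. How 11.2.2 classifies a reaction to a repeat course.** Every such reaction occurs more than 3 months after randomisation.

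| Time from randomisation | Category under 11.2.2 |
|---|---|
| Between 3 and 6 months | neither acute nor late |
| From 6 months | late, however soon after the repeat course |

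**5. 10.1 against 10.4.** A radiotherapy-related grade 3 hospitalisation at, say, month 9 is not covered by the grade threshold in 10.1 but appears to be covered by 10.4. Section 10.4 refers back to the earlier text, so it is unclear whether it is meant to be wider.

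**The case against.** The strongest reply is that 8.4 does not stop toxicity collection; it relaxes visit timing and is silent on toxicity. Progressed patients are still in follow-up, AEs count throughout follow-up, all AEs go on a CRF, and toxicity is assessed at each clinic visit. This stands, and it rules out reading 8.4 as an instruction to cease monitoring. It does not close the gap: 10.3 sets no timetable after progression and asks for the worst grade since the last visit, while 8.4 releases the protocol visits.

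A reader might also infer that all acute harm from repeat courses goes unmonitored, or that the safety criterion is blind after progression. The documents support neither. Radiotherapy-related grade 4 or higher events are reportable to 5 years, with no exception for progression or repeat courses. The criterion concerns the experimental arm alone, so unequal observation between arms does not bear on it. Its formal reviews use patients followed for 6 months, when about 82% of SBRT patients would be event-free. The criterion is exposed mainly to misclassification, which would raise its count.

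Nor can repeat SBRT be called the highest-risk exposure on this text. Section 9.1.6 requires composite dose assessment against all normal-tissue constraints and bars re-irradiation of SBRT-treated lesions. The end-of-treatment visit in 8.3.1 is tied to the last SBRT fraction and does not expressly exclude a repeat course, although the schedule in 8.8 shows that visit once.

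**Conclusion.** The concern holds for scheduled capture of lower-grade toxicity and for the dating of repeat-course toxicity. After progression the plan does not secure CTCAE/RTOG grading below the serious-event threshold, and its sections conflict on whether grading continues. At most 18% (SBRT) and 23% (SOC) of patients could be affected by month 6, and 54% and 65% by month 24, given exponential PFS and the protocol's planning values.

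It would be too strong to say that late harm is missed in most patients. Even at these upper bounds, the SBRT arm passes one half only at about 21 months and the SOC arm at 16 months; at 1 year, the protocol's time point of interest for time-to-event endpoints, 68% of SBRT patients are event-free.

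The misclassification of repeat-course reactions follows from the definitions and needs no distributional assumption. How many patients it touches cannot be estimated: the documents give no expected number of repeat courses, and the 3-lesion cap limits it. The point merits a wording change; it does not undermine the primary analysis.

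**What to change.** - **8.4:** add CTCAE/RTOG grade to the data entered on the eCRF after progression, taken from whichever local visit falls nearest each existing time point. Make clear that this also applies to patients routed there by 8.5.
- **11.2.2:** date acute and late toxicity of a repeat course from that course, and tabulate it separately for the IDMC, so that the 5% criterion is not fed by misdated acute events.
- **10.1 and 10.4:** state whether reporting after day 90 covers radiotherapy-related grade 4 or higher events or all radiotherapy-related SAEs, and how it applies to repeat courses.

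The cost is protocol wording, eCRF pages and modest extra data entry for patients already followed for widespread disease and survival. Grading from local visits will be less complete than from protocol visits. No added tests, visits or treatment rules are proposed.

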8.5 Discontinuation from treatment

Participants may discontinue from trial treatment at any time at their own request, or they may be discontinued at the discretion of the Principal Investigator. Reasons for discontinuation may include:

- Disease progression or recurrence
- Unacceptable toxicity
- Pregnancy.

Participants who discontinue treatment should continue to be followed up as per section 8.4.

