8.3.2 Breast Primary Patients

The following assessments should be conducted for all breast primary patients at each follow up visit (Months 3, 6, 9, 12, 15, 18, 21, 24, 30, 36, 42, 48, 54 and 60 months post randomisation):

- CT scan of chest, abdomen and pelvis. This may be replaced by FDG PET/CT scan as long as the CT scan is of diagnostic quality, or whole body dwMRI if locally available.
- Tumour assessment according to RECIST v.1.1 criteria, where possible. In instances where RECIST assessment is not possible assessment by other methods should be considered or a clinical assessment of widespread progression should be performed. Assessment of tumour marker Ca 15-3 (where locally available).
- Physical examination including WHO performance status, weight and height.
- Assessment of late toxicity using NCI CTCAE v.4.0 and RTOG (RTOG is excluded for the first 3 month post randomisation).

In addition the following assessments should be performed:

Month 6 post randomisation

- Full blood count, urea, electrolytes and LFTs (ALT/AST, bilirubin, albumin).

Months 3, 6, 12, 18 and 24 post randomisation

- Quality of life questionnaire (EORTC QLQ C30 and EQ5D)

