8.8 Schedule of assessments

| Visit/Assessments/ Procedures | Pre-randomisation | Pre-treatment | End of trial treatment for SBRT + SOC group or equivalent for SOC group | Time from randomisation | | | | | | | | | | | | | |
|--|-------------------|---------------------------------------|---|-------------------------|-----|------------------|------|------------------|------------------|------------------|------|------------------|------------------|----------------|------------------|----------------|------------------|
| | Within 42 days | Following confirmation of eligibility | SBRT + SOC group: within +/- 7days of last SBRT treatment SOC only group: within 6 weeks after randomisation | 3 M | 6 M | 9 M | 12 M | 15 M | 18 M | 21 M | 24 M | 30 M | 36 M | 42 M | 48 M | 54 M | 60 M |
| Informed consent | X | | | | | | | | | | | | | | | | |
| Histological confirmation of primary breast, prostate or NSCLC | X* | | | | | | | | | | | | | | | | |
| Complete medical history | X | | | | | | | | | | | | | | | | |
| Physical examination including WHO performance status, body weight, height, blood pressure (BP at baseline only) | X | | X | X | X | X | X | X | X | X | X | X | X | X | X | X | X |
| Tumour primary assessment using RECIST v.1.1 criteria | X | | | X ^{B,L} | X | X ^{B,L} | X | X ^{B,L} | X ^{B,L} | X ^{B,L} | X | X ^{B,L} | X ^{B,L} | X ^B | X ^{B,L} | X ^B | X ^{B,L} |
| Concomitant therapy assessment | | X | X | | | | | | | | | | | | | | |
| Full blood count, urea and electrolytes, LFTs | | X | | | X | | | | | | | | | | | | |
| Pregnancy test (for women of childbearing potential) | X | | | | | | | | | | | | | | | | |
| Symptom assessment using NCI | | X | X | X | X | X | X | X | X | X | X | X | X | X | X | X | X |

| Visit/Assessments/ Procedures | Pre-randomisation | Pre-treatment | End of trial treatment for SBRT + SOC group or equivalent for SOC group | Time from randomisation | | | | | | | | | | | | | |
|---|-------------------|---------------------------------------|---|-------------------------|----------------|----------------|----------------|----------------|----------------|----------------|----------------|----------------|----------------|----------------|----------------|----------------|----------------|

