11.2.4 Statistical analysis plan

Analyses will be according to the intention-to-treat method. Time to event endpoints will be presented using Kaplan Meier methods with treatment effects presented as relative and absolute estimates. Hazard ratios will be derived from Cox proportional hazards models stratified by disease site. The time point of interest is 1 year from randomisation. The log rank test will be used to compare treatment groups stratified by disease site. For PFS, patients who are event free at time of analysis will be censored using the date of last disease assessment (imaging for breast, NSCLC and PSA assessment for prostate). An appropriate alternative method will be used if there is evidence of non-proportional hazards.

Acute and late toxicity will be summarised as frequencies and percentage at each time point. Non-haematological grade 2 or greater (G2+) toxicities related to SBRT treatment are of primary interest. The proportion experiencing G2+ will be presented by treatment group and comparisons made between treatments using Fishers exact tests, separate comparisons will be made of acute and late toxicity.

Quality of life data will be analysed using standard algorithms to derive scores and handle missing data according to the EORTC scoring manual. Descriptive statistics (median, IQR, range) will be presented by treatment group at each time-point. Statistical comparisons will be made at 12 and 18 months. Analyses to account for the longitudinal nature of the data may also be used.

A planned exploratory analysis will be performed to investigate the treatment effect in each primary site subgroup. This will be summarised with a hazard ratio and compared in each subgroup to look for consistency of effect (accepting that there will be little power for a formal test of heterogeneity). There will be very limited power and much uncertainty about these estimates, and therefore they will be interpreted with caution.

Further details of analysis methods will be specified in a Statistical Analysis Plan in accordance with ICR-CTSU Standard Operating Procedures.

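### Section 8.5 sends every patient who stops treatment to the post-progression follow-up of Section 8.4, which conflicts with the PFS schedule that Section 8.3 sets for all patients

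*Protocol*

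**What the plan says.** Section 8.5 opens: "Participants may discontinue from trial treatment at any time at their own request, or they may be discontinued at the discretion of the Principal Investigator". The reasons it lists are progression or recurrence, unacceptable toxicity and pregnancy. One follow-up instruction then covers every case: "Participants who discontinue treatment should continue to be followed up as per section 8.4".

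Section 8.4 is the procedure at disease progression. It starts with how a progression event is established, and continues: "Following progression, participants will continue to be followed-up for FFWM and overall survival". On timing it says: "Imaging and visits following progression can be according to local practice and do not need to follow the protocol specified visit time points". The information it asks sites to enter afterwards is widespread-disease status and survival status. It contains no PFS schedule.

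The scheduled imaging, PSA and RECIST assessments are in Section 8.3, one subsection per tumour type. The breast subsection begins: "The following assessments should be conducted for all breast primary patients at each follow up visit". The NSCLC and prostate subsections are built the same way. All times run from randomisation, with no condition on treatment status. Section 8.5 does not mention Section 8.3.

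PFS is the primary endpoint (11.2.1). Section 11.2.4 states: "Analyses will be according to the intention-to-treat method", and censors patients who are event free at the analysis at their last disease assessment.

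**The concern.** Most of the reasons for stopping in Section 8.5 are not PFS events. A patient who stops for toxicity is still at risk of progression and still counts in the intention-to-treat comparison. The only follow-up instruction written for that patient points to a section that does not call for scheduled scans.

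A site that takes 8.5 at its word may scan later than the schedule or not at all. Progression is then dated late or missed, and the patient may be censored at an old assessment. The late-toxicity and quality-of-life assessments are also in 8.3, so a patient who stops because of toxicity could leave the late-toxicity schedule too.

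The direction of any bias depends on who is caught. The safety section speaks of "trial treatment, which for the purposes of this trial will be SBRT", and the assessment schedule (8.8) labels one visit "End of trial treatment for SBRT + SOC group or equivalent for SOC group". On that meaning, stopping trial treatment happens mainly in the SBRT arm, and late detection there favours SBRT. The PFS result feeds the phase III decision at the 10% and 20% levels (11.1.2). An analysis plan cannot repair this afterwards, because it cannot recover scans that were never made.

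**Working it through.** **1. The sections side by side**

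| Section | Who it addresses | What it requires |
|---|---|---|
| 8.3 | All patients of each tumour type | Imaging, PSA, RECIST, late toxicity and QoL at fixed months from randomisation |
| 8.4 | Patients at and after progression | Widespread disease and survival; visits and scans by local practice |
| 8.5 | All who stop treatment, for any reason | Follow-up under 8.4 |

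For a patient who stops without progression, 8.3 and 8.5 give different instructions. The relaxation in 8.4 is worded for the time after progression, so read strictly it does not reach this patient.

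**2. The plan's own event number.** Inputs from 11.1.2: one-sided α = 0.20, power 80%, HR 0.75, 1:1 allocation.

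- Schoenfeld: 4(0.8416 + 0.8416)² / (ln 0.75)² = 4 × 2.833 / 0.0828 = 137.
- Freedman: (1.75/0.25)² × 2.833 = 49 × 2.833 = 139.
- The stated 138 is reproduced. Power at 138 events is 80.2%.

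**3. Events exposed.** The protocol gives no discontinuation rate, so 5%, 10% and 15% of 115 SBRT patients are assumptions. Take exponential PFS with a control median of 16 months, HR 0.75, 24 months of uniform accrual (a) and 12 months of further follow-up (f). The hazard in the SBRT arm is λ = 0.75 × ln 2 / 16 = 0.0325 per month. The chance of an event by the analysis is 1 − (e^(−λf) − e^(−λ(a+f))) / (λa) = 1 − (0.677 − 0.310) / 0.780 = 0.53.

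| Assumed stopping | Patients of 115 | PFS events exposed | Power if those events are lost |
|---|---|---|---|
| 5% | 6 | 3 | 79.7% |
| 10% | 12 | 6 | 79.1% |
| 15% | 17 | 9 | 78.6% |

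The largest loss is 80.2 − 78.6 = 1.6 points.

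**4. Delayed detection in the SBRT arm only.** This was a log-rank simulation with 115 per arm, a 16-month median in both arms (no true effect) and 4,000 runs. Stoppers have average prognosis and their event times are shifted by 3 or 6 months, which is one or two missed three-monthly visits. The entries are the one-sided error at nominal 20%.

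| Assumed stopping | 3-month delay | 6-month delay |
|---|---|---|
| none | 20% | 20% |
| 5% | 20% | 24% |
| 10% | 24% | 28% |
| 15% | 26% | 32% |

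The average HR estimate falls from 1.00 to between 0.99 and 0.94. The Monte Carlo standard error is √(0.2 × 0.8 / 4000), about 0.6 points. The simulation delays deaths as well as progressions. Deaths are still recorded under 8.4, so it somewhat overstates the effect. A separate run with a 3-month delay and stoppers at twice the hazard gave 22%, 24% and 25%.

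**5. When the effect disappears.** With 2% stopping, even permanent censoring of the stoppers leaves the error at 10% and 20% for those nominal levels. With equal stopping in both arms, permanent censoring gives HR 1.00 and again about 10% and 20%.

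**The case against.** The strongest reply is that nothing is waived. Section 8.4 frees visits and imaging only after progression, Section 8.3 covers all patients, and the schedule in 8.8 makes no exception for discontinuers. A careful site would keep scanning. This stands: the text contradicts itself and does not order PFS assessment to stop. It does not remove the point, because 8.5 is the specific rule for this situation and points to the wrong section.

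A reader might go further and infer that stoppers are censored when they stop, in the experimental arm only, with a poor prognosis. A simulation on those terms (15% stopping, twice the hazard, censored for good at month 2) gives false-positive rates of about 21% at the 10% level and 36% at the 20% level. The documents do not support that reading:

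- Deaths remain PFS events, and widespread disease is still followed with local imaging, so permanent censoring is a worst case.
- The 15% is the complement of the 85% delivery target in 11.2.5. Shortfalls against that target also include patients with new widespread disease, who already have a PFS event, and patients treated outside the dose constraints, who did not stop.
- Table 1 allows at most 21 days for a course, so there is little time to stop part-way.
- The doubled hazard has no source in the protocol.
- The SBRT meaning of trial treatment comes from the safety section. Section 9, under the same term, includes standard of care, so stops of systemic therapy in either arm could also be caught. That would make the effect less one-sided but could expose more patients.

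On toxicity, radiotherapy-related events of grade 4 or above are still reported on SAE timelines up to 5 years (10.1). What is exposed is the scheduled grading at lower grades.

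**Conclusion.** The point holds as an internal contradiction in the instructions that govern ascertainment of the primary endpoint. Section 8.5 directs patients without progression to a post-progression procedure, against the schedule in 8.3.

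The size is uncertain because no discontinuation rate is given. With 5-15% stopping in the SBRT arm alone and detection delayed by 3-6 months, all assumed, the one-sided 20% error becomes about 20-32%, in favour of SBRT. With rarer or balanced stopping there is little or no inflation. If the events are lost rather than delayed and stoppers have average prognosis, power falls by less than 2 points. A heavier imbalance in the SBRT arm is plausible but is an inference. A bias confined to that arm, or a false-positive rate of 21% or 36%, is not established.

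**What to change.** Reconcile Sections 8.3, 8.4 and 8.5 by changing the reference in 8.5. Suggested wording: Participants who discontinue, or never start, their allocated treatment and have not progressed continue all assessments in Section 8.3 at the protocol time points until a PFS event; Section 8.4 applies only after progression. State in the same place whether trial treatment here means SBRT alone or also standard of care.

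The cost is a sentence or two in the next amendment and a note to sites. It adds no visits beyond those already scheduled for every patient and changes no stated sample size or event number.
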